### DESIGN, SETTING, AND PARTICIPANTS

This study was performed between May 2016 and September 2019 at a single academic medical center. Adult women were eligible to participate if they were scheduled to undergo elective surgery by two female pelvic medicine and reconstructive surgery or minimally invasive gynecology surgery staff that would require intraoperative cystoscopy, including POP repair, mid-urethral sling placement (MUS), hysterectomy, and complicated excision of endometriosis. Cystoscopy is routinely performed with these procedures in our practice. Exclusion criteria included history of neurogenic bladder, recurrent UTIs, nephrolithiasis, congenital urogenital anomaly, allergy to neomycin or polymyxin, pregnancy, or surgery planned to include intradetrusor onabotulinumtoxin A injection, mesh excision, or fistula repair. Women were excluded if they were found to have a positive urine culture on routine preoperative testing, independent of symptoms, or from an intraoperative urine sample. All subjects provided written informed consent. Participation in this study did not have any direct benefit to individual subjects.

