### INTERVENTION, RANDOMIZATION, AND BLINDING

Patients were randomized 1:1 at the time of surgery into two groups based on the type irrigation to be used with intraoperative cystoscopy: control (normal saline) or antibiotic (Neosporin G.U. [200,000 U polymyxin B sulfate +40 mg neomycin sulfate] in 1 L NS). The randomization scheme was assigned by a statistician using randomization software in blocks of 10. Allocation was concealed in an opaque envelope until the time of randomization. The patients and attending surgeon, who performed all evaluation and treatment of postoperative UTIs, remained blinded. Neosporin G.U. (Pfizer, 200,000 U polymyxin B sulfate 40 mg neomycin sulfate) is Food and Drug Administration approved for short-term use as a bladder irrigant to prevent bacteriuria associated with the use of indwelling catheters. The prepared solution is completely clear, bactericidal, and used as indicated, neomycin and polymyxin B are absorbed in clinically insignificant quantities. A neomycin or polymyxin solution was used in Hares' 1981 cystoscopy irrigation study, has been used successfully in spinal cord injury patients with bacteriuria, and is well tolerated. Additionally, the medication is inexpensive and readily available in our operating room pyxis.

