## STUDY PROTOCOL

At the time of surgery, the randomization allocation envelope was opened by the surgical fellow. If indicated, this individual prepared the antibiotic solution by injecting 1 ml of neomycin or polymyxin into 1 L normal saline. The fellow remained independent of postoperative UTI diagnosis and treatment for study participants. The steps of the surgery remained standard; the study protocol made no alterations to usual care involving patient preparation, intravenous antibiotics, and instrumentation. We routinely use cefazolin for antibiotic prophylaxis for all surgeries, with the addition of metronidazole for hysterectomy in premenopausal patients, except in the case of associated allergies. Upon routine urinary catheter insertion, a urine sample was collected and sent for culture. Patients with a positive intraoperative urine culture were later excluded from analysis.

Intraoperative cystoscopy was performed in normal fashion with the previously designated bag of irrigation fluid. At the completion of cystoscopy, the bladder was drained as per standard operating procedure. To determine the volume of fluid used during cystoscopy, the fluid bag was weighed before surgery and again after cystoscopy. A foley catheter was replaced per surgeon discretion. Upon hospital discharge, standardized post-operative instructions were given to all patients, including signs and symptoms of infections or other concerning postoperative sequelae.

Postoperatively, patients were called at three time points (3 days, 2 weeks, and 4 weeks after surgery) to assess for urinary complaints and adverse events, including patient-reported diagnosis and treatment of UTI. Subjects were treated for postoperative UTI per attending surgeon discretion.

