## OUTCOME MEASUREMENTS

The primary outcome was the rate of postoperative UTI within 6 weeks after surgery. The Center for Disease Control and Prevention's definition of a symptomatic UTI was adapted to include the following: (1) at least one sign or symptom accompanied by positive urine culture with  $\geq 105$  colony-forming units/ml, (2) symptomatic UTI with clinician decision to treat as reported by the patient, or (3) at least one sign or symptom with positive urine dipstick (UA). Timing of diagnosis was recorded as either the date of the positive urine culture or the timing of the postoperative phone call when the patient reported treatment of a UTI (3 days, 2 weeks, or 4 weeks after surgery). A sensitivity analysis was performed of UTIs treated within 2 weeks of surgery and any adverse effects related to the use of antibiotic irrigation. We also evaluated outcomes in the subgroup who had a vaginal prolapse repair procedure, which was previously reported to be at highest risk for postoperative UTI.

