## STATISTICAL ANALYSIS

Based on 20.3% incidence of postoperative UTI, we determined that a sample size of 186 would provide 80% power to detect a 50% absolute reduction in postoperative UTI rates at a two-sided  $\alpha = .05$ . To account for an estimated 30% dropout rate with positive intraoperative urine culture or loss to follow up, we adjusted the total sample size to 242 patients total, with 121 subjects in each study arm.

Data was collected in our institutional REDCap database, and statistical analysis was performed with Stata version 15.1 (StataCorp). Covariates included in the analysis were patient-specific characteristics and medical comorbidities (age, race, obesity, smoking status, menopausal status, and history of Type 2 diabetes, recurrent UTIs, thyroid disease, asthma, hypertension, reflux disease, depression, or anxiety) and volume of cystoscopy fluid used. Surgeries were characterized as primary vaginal or laparoscopic, and all concurrent procedures were noted. The randomized groups were compared using Pearson's  $\chi^2$  test for categorical variables and the Student's t test for normally distributed continuous variables. Multivariable logistic regression analysis was used to adjust for possible confounding variables impacting the effect of antibiotic irrigation on postoperative UTI rates. Covariates significant on univariate analysis with  $p < .2$  or with notable clinical relevance were included in the logistic regression. All results yielding  $p < .05$  were deemed statistically significant.

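### Attending surgeon, known before randomisation and plausibly prognostic, is in neither the primary test nor the listed covariates; stratifying by it is a small, nearly free gain

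*Combined protocol and SAP*

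**What the plan says.** All references are to the combined protocol and SAP.

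- **Analysis.** Statistical Analysis compares categorical variables between arms by Pearson's chi-square, with no stratification. It then states: "Covariates included in the analysis were patient-specific characteristics and medical comorbidities". The list runs from age and race through asthma, thyroid and reflux disease to fluid volume. Attending is not on it. A covariate enters the logistic model if its univariate p-value is below .2 or if it is judged clinically relevant.
- **Surgeons.** Design, Setting, and Participants recruits women "scheduled to undergo elective surgery by two female pelvic medicine and reconstructive surgery or minimally invasive gynecology surgery staff".
- **Allocation.** Intervention, Randomization, and Blinding says "Patients were randomized 1:1 at the time of surgery into two groups" and "The randomization scheme was assigned by a statistician using randomization software in blocks of 10". No stratification factor is given.
- **Role of the attending.** The same section says "The patients and attending surgeon, who performed all evaluation and treatment of postoperative UTIs, remained blinded". Study Protocol adds "Subjects were treated for postoperative UTI per attending surgeon discretion" and also leaves catheter replacement to the surgeon.
- **Outcome.** Outcome Measurements counts a UTI by any of three routes: "at least one sign or symptom accompanied by positive urine culture" above a colony threshold; "symptomatic UTI with clinician decision to treat as reported by the patient"; or a sign or symptom with a positive dipstick.

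**The concern.** The attending is fixed before allocation and known for every woman. The documents give several reasons why UTI rates might differ between attendings:

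- The attending evaluates every suspected UTI, and no routine postoperative culture or dipstick is described.
- The attending decides on treatment, and a decision to treat is one of the three outcome routes.
- The attending decides whether a catheter is replaced.
- Case mix may differ, since eligible surgery ranges from prolapse repair to endometriosis excision, and Outcome Measurements cites prolapse repair as carrying the highest UTI risk.

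A factor of this kind is a natural stratifier. Leaving it out means that a chance surplus of one attending's patients in one arm goes uncorrected, and that between-surgeon variation stays in the error term. At stake are a little precision and some protection against an unlucky allocation.

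**Working it through.** **Inputs from the documents.** Control rate 20.3%; two-sided alpha .05; evaluable target 186; 242 randomised with 30% expected loss, so 242 x 0.70 = 169 evaluable. The planned effect is worded as a 50% absolute reduction, which is impossible from 20.3%. It is read here as relative, giving 10.15%.

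**Inputs that are assumptions.** Two attendings, equal caseloads, and the control rate of each. None of these is settled by the documents, so a range is shown.

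**The plan's own figure.** With p1 = 0.203, p2 = 0.1015 and mean 0.15225, the pooled formula gives n per arm = [1.96 x sqrt(2 x 0.15225 x 0.84775) + 0.842 x sqrt(0.1618 + 0.0912)]^2 / 0.1015^2 = 196, or 392 in total. The stated 186 is not reproduced. Power with 93 per arm is 48.7%, which is why the powers below sit near 50% and not 80%. That is a separate and larger matter and lends no support to this point.

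**Step 1: size of chance imbalance.** The SD of the between-arm difference in one attending's share is sqrt(0.5 x 0.5 x 4/N):
- N = 169: sqrt(1/169) = 0.077
- N = 186: sqrt(1/186) = 0.073

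The 95% range at N = 169 is about ±15 points.

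**Step 2: how much variance surgeon could explain.** With equal caseloads and a gap g between attendings, the control-arm share is (g/2)^2 / (0.203 x 0.797):
- gap 10 points: 0.0025/0.1618 = 1.5%
- gap 20 points: 0.0100/0.1618 = 6.2%
- gap 30 points: 0.0225/0.1618 = 13.9%

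Only a very large gap leaves much to recover.

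**Step 3: power.** Simulated trials used individual 1:1 allocation and a 50% relative reduction. The 186-women rows used unstratified blocks of 10 and 20,000 trials each. The 169-women rows used 200,000 trials each.

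| Women | Assumed control rates (%) | Chi-square power (%) | CMH power (%) | Change (points) |
|---|---|---|---|---|
| 186 | 20.3 / 20.3 | 49.3 | 49.1 | -0.2 |
| 186 | 25.3 / 15.3 | 48.5 | 48.7 | +0.2 |
| 186 | 30.3 / 10.3 | 49.3 | 50.5 | +1.2 |
| 186 | 35.3 / 5.3 | 49.2 | 53.1 | +3.9 |
| 169 | 25.6 / 15.0 | 45.9 | 46.0 | +0.1 |
| 169 | 30.6 / 10.0 | 45.8 | 47.2 | +1.4 |
| 169 | 35.6 / 5.0 | 45.6 | 49.4 | +3.8 |

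The changes of 0.2 points or less are negligible.

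**Step 4: bias and type I error.** With no treatment effect at 186 women, both tests rejected in 4.9 to 5.1% of trials in every scenario, and the mean risk difference was within 0.1 point of zero. The omission therefore damages neither the estimate on average nor the overall error rate.

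**Step 5: the unlucky allocation.** At 169 women about 6.5% of trials have a surgeon imbalance of 14 points or more. Within those trials the chi-square's type I error was about 6%, 8% and 12 to 13% for assumed gaps of about 10, 20 and 30 points. The stratified test stayed near 5%.

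**The case against.** Three stronger readings are tempting, and the documents support none of them.

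1. *A reader might infer that the treatment comparison is biased by surgeon.* It is not. Women are individually randomised and the attendings are blinded, so each attending's threshold applies to both arms alike in expectation. Step 4 agrees.
2. *A reader might infer that the attending's discretion decides who is counted.* A symptomatic woman with a positive culture or dipstick counts whether or not she is treated; only the second route needs a decision to treat. The attending's control of evaluation may also affect who is tested, but the documents do not describe how tests are ordered, nor what share of events would arise by the second route alone.
3. *A reader might work out a large shift in the effect.* Multiplying a 15-point imbalance by a 20.6-point gap gives 0.15 x 0.206 = 3.1 points, about 30% of the planned 10.15. That pairs the edge of the 95% range with an assumed threefold rate difference, and applies the control-arm gap to both arms. With rates halved by treatment the same imbalance gives 0.075 x 0.206 + 0.075 x 0.103 = 2.3 points. A one-SD imbalance with no treatment effect gives 0.077 x 0.206 = 1.6 points, against a standard error of sqrt((0.1618 + 0.0912)/84.5) = 5.5 points.

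The defence has further fair points. The clinical-relevance clause could admit attending. Surgical route and concurrent procedures are recorded, and a prolapse subgroup is planned, so part of any case-mix difference can be captured directly. The sentence on surgeons is ambiguous about their number and does not say that their specialties differ. Silence on stratified randomisation does not prove that surgeon was ignored. These points limit the finding but do not remove it: the clause does not name attending, it leaves model entry to later judgement, and it does nothing for the unstratified primary test.

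**Conclusion.** The point stands as a minor refinement. Attending is known before allocation and plausibly prognostic, yet it is absent from the primary test and the listed covariates, and no stratified allocation is stated. Nothing here is an error of level or a bias.

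The benefit is about 0, 0, 1 to 2 and 4 points of power for assumed gaps of 0, 10, 20 and 30 points, plus a type I error that stays near 5% when the allocation happens to be unbalanced on surgeon. The 4-point gain needs one attending near 35% and the other near 5%, which nothing in the documents suggests. All of this rests on two attendings with equal caseloads. If their rates are alike, the gain is nil.

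**What to change.** - For the primary outcome, replace the unstratified Pearson chi-square with a Cochran-Mantel-Haenszel test stratified by attending.
- Enter attending in the logistic model as a fixed factor regardless of its univariate p-value.
- State how many attendings took part, and whether the randomisation list was stratified by surgeon.
- If the primary analysis has already been done, keep it as specified and report the stratified test and adjusted model as a sensitivity analysis, labelled as added afterwards.

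The cost is a sentence or two in the SAP and no new data. With two attendings the model loses one degree of freedom; with more, one fewer than their number. If the attendings have similar rates, nothing is gained and at most a fraction of a point of power is lost.

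### The plan calls every p<.05 significant and tests the 6-week primary outcome two ways without saying which test decides the efficacy conclusion

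*Combined protocol and SAP*

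**What the plan says.** One primary outcome is named under Outcome Measurements: the UTI rate over the first 6 weeks. Four between-arm comparisons of UTI follow from the text.

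1. Under Statistical Analysis, the arms are compared by Pearson's chi-square for categorical variables.
2. The same section adds an adjusted analysis of the irrigation effect: "Multivariable logistic regression analysis was used to adjust for possible confounding variables". Covariates enter if univariate p<.2 or if judged clinically relevant.
3. Under Outcome Measurements: "A sensitivity analysis was performed of UTIs treated within 2 weeks of surgery".
4. In the same place: "We also evaluated outcomes in the subgroup who had a vaginal prolapse repair procedure".

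The Statistical Analysis section closes with the rule that all results below .05 "were deemed statistically significant". It gives no order of testing and no multiplicity adjustment, and it does not say whether the unadjusted or the adjusted 6-week comparison is primary. The two-sided .05 appears only in the sample-size statement.

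**The concern.** The primary outcome has two eligible tests. The content of the second is settled only after the data are seen, because of the p<.2 screen and because clinical relevance is not defined. If one test falls below .05 and the other does not, the plan does not say which governs. Allowing either to count gives a false-positive rate above the .05 stated for the primary outcome.

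The 2-week and subgroup comparisons come under the same threshold. The 2-week analysis changes the outcome window, so it can be positive when the 6-week result is not. The subgroup is introduced as the group at greatest risk, which would make a benefit confined to it easy to present after a null overall result. What is at stake is whether a reader can tell a confirmatory finding from a supportive one.

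**Working it through.** **Inputs from the plan.** Two-sided α = .05; control UTI rate p = 20.3% ("20.3% incidence of postoperative UTI"); 186 analysable women randomized 1:1, so 93 per arm ("a sample size of 186 would provide 80% power").

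**Inputs assumed, because the plan does not give them.** Correlation r between the unadjusted and adjusted test statistics: 0.95 (range 0.84-0.98). Share f of UTIs occurring by 2 weeks: 60% (range 30-85%). Share s of women in the prolapse subgroup: 50% (range 30-80%).

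**Step 1: the plan's own error rate.** One test at two-sided .05 has a 5% false-positive rate, half of it (2.5%) favouring the irrigant. Simulated null trials with 93 per arm gave 4.7% and 2.4% for the chi-square, so a single test delivers the stated level. (The figure of 186 itself is not reproduced: reading the stated effect as a halving, 20.3% to 10.15%, the usual formula needs 196 per arm. That is a separate matter and does not affect error rates under no effect.)

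**Step 2: two tests of the 6-week outcome.** With Z1 unadjusted and Z2 adjusted, bivariate normal with correlation r:

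- either direction: 1 − Pr(|Z1| ≤ 1.96 and |Z2| ≤ 1.96)
- favouring the irrigant: 1 − Pr(Z1 ≤ 1.96 and Z2 ≤ 1.96), signed so that positive means benefit

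| r | Either direction | Favouring the irrigant |
|---|---|---|
| 0.84 | 7.5% | 3.8% |
| 0.90 | 7.0% | 3.5% |
| 0.95 | 6.5% | 3.2% |
| 0.98 | 5.9% | 3.0% |

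Simulated trials with the p<.2 screen gave 6.45% in either direction where the correlation was 0.95, and 7.7% with strong covariates (correlation 0.84).

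**Step 3: all four tests.** Number them 1 unadjusted, 2 adjusted, 3 two-week, 4 subgroup.

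- r13 = √[f(1 − p)/(1 − fp)] = √[0.6 × 0.797/(1 − 0.1218)] = √(0.4782/0.8782) = 0.738
- r14 = √s = √0.5 = 0.707
- r34 = 0.738 × 0.707 = 0.522
- r23 = 0.95 × 0.738 = 0.701; r24 = 0.95 × 0.707 = 0.672

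Two million draws from this four-variate normal give 12.2% for at least one two-sided p<.05 and 6.1% for at least one favouring the irrigant. Four independent tests would give 1 − 0.95⁴ = 18.5%, which is a ceiling.

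**Step 4: range.** In simulated trials with 93 per arm:

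| f | s | Either direction | Favouring the irrigant |
|---|---|---|---|
| 30% | 30% | 14.0% | 7.0% |
| 50% | 50% | 12.3% | 6.2% |
| 70% | 50% | 11.7% | 5.7% |
| 80% | 80% | 10.3% | 5.0% |

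With 121 per arm, f = 60% and s = 50%, the results were 12.7% and 6.4%. The normal approximation over its full grid gave 9.9-14.4% and 5.0-7.2%.

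**Step 5: a null chi-square followed by another significant result.** 12.2% − 5.0% = 7.2% of null trials in either direction; by symmetry half of these, 3.6%, would favour the irrigant.

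**The case against.** The strongest reply is that the closing sentence only defines when a p-value is called significant. It does not say that one significant result establishes efficacy. The plan already ranks its analyses: one primary outcome, a 2-week analysis labelled as sensitivity, and a prolapse analysis labelled as a subgroup. Most of the rise to 12% comes from treating those two as separate routes to a claim. The ambiguity left within the primary outcome moves the rate only from 5% to about 6.5%. The plan also promises no family-wise error rate.

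Much of this stands. A reader might infer that a useless irrigant has a 12% chance of being declared effective. The documents do not support that. The tests are two-sided, about half of the false positives would point to harm, and no rule turns any single win into a declaration of efficacy. A reader might also infer that the plan rules out treating the secondary analyses as exploratory. It does not; it leaves their standing unstated.

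The reply does not remove the point. The labels do not limit the blanket rule, and they say nothing about which of the two 6-week tests is decisive.

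**Conclusion.** The point holds as a matter of what may be concluded from which test. The firm part is that the primary outcome has two tests and no stated decision between them. That costs about 1.5 percentage points two-sided (6.5% against 5%) at a correlation of 0.95, and between about 1 and 2.5 points over correlations of 0.98 to 0.84.

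The larger figures, about 12% (10-14%) in either direction and about 6% (5-7%) favouring the irrigant, against 5% and 2.5% for one named test, apply only if a reader gives all four results equal weight. They also rest on an early-event share and a subgroup size that the documents do not report. The excess over a single test persists across the ranges tried.

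**What to change.** Replace the closing significance sentence with:

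> *The efficacy conclusion rests on one test, the unadjusted between-arm Pearson chi-square comparison of UTI within 6 weeks at two-sided .05. The adjusted model, the 2-week sensitivity analysis and the prolapse subgroup are supportive, are reported as estimates with 95% confidence intervals, and do not on their own support a claim of efficacy.*

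The choice should not be justified by saying that the sample size was built on the chi-square, because the plan names no test for that calculation. The unadjusted test is preferred here because its content is fixed before the data are seen.

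This returns the error rate for the efficacy conclusion to 5% two-sided, and no analysis is dropped. Testing all four at .0125 is not needed and would overcorrect: the same model gives 3.4% two-sided.

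The cost is one sentence, and a p<.05 in a supportive analysis can no longer be reported as a positive finding. Because the text describes a completed study, the designation should be reported openly as a clarification of how results are interpreted, not as a pre-specified rule.
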